Impact of Graduating to Resilience on Child Development in Uganda

Pre-Analysis Plan

IPA-2022-UG
August 31, 2022

Background

This study is an intervention trial that aims to estimate the impact of the Graduating to Resilience (G2R) program on child development in Uganda. In previous trials, the G2R program has generated large, positive impacts on household assets, consumption, income and food security. The investigators will revisit a sample of households enrolled in a G2R trial conducted in Uganda in 2019-2021 (AEARCTR-0004080) and assess children born during the intervention period.

A large body of evidence demonstrates that early exposure to poverty and related adverse experiences, including toxic stress, malnutrition, and psychosocial deprivation, impedes child brain development and skill formation [1,2]. A similarly robust literature shows that the negative effects of poverty-related adversity can be mitigated through early-life intervention [3]. The holistic nature of the G2R program may be particularly beneficial to early childhood development.

Randomization

In the G2R trial in Uganda, villages were randomly assigned to either treatment or control villages. Within treatment villages, participants were randomly assigned at the household-level to one of three intervention conditions or a control condition:

- T1, “Individual, asset”: consumption support, cash asset transfer, coaching in individual household visits
- T2, “Group, asset”: consumption support, cash asset transfer, coaching in group setting and all other aspects of program
- T3, “Individual, no asset”: consumption support, *no* cash asset transfer, coaching in individual household visits and all other aspects of program
- C1, “Control in treatment villages”: no intervention

For this study, investigators will revisit T1, T2, and C1 households within treatment villages. Based on the results of the G2R trial, within-village spillovers are expected to be minimal.

Empirical strategy

In the main analysis, the investigators will estimate average treatment effects of the G2R program on all primary and secondary outcomes using an intention-to-treat approach. The investigators will combine T1 and T2 groups into a single intervention group for the analysis. The results of the G2R trial indicate that impacts on household assets, consumption, income, and food security were similar in T1 and T2.

The investigators will also examine heterogeneity in treatment effects by the duration of program exposure *in utero*. The relative contributions of poverty-related adversity experienced *in utero* versus post-birth on child development is an important research question. The investigators will also estimate impacts within refugee and host (i.e., non-refugee) strata, as the population of the G2R trial was drawn from these two communities.

Analysis

The investigators will fit a set of unadjusted and adjusted linear regression models to estimate average treatment effects. All models will include variables used for stratification in the original randomization procedure. Adjusted models will include the following additional covariates to improve precision: child age in months and gender; caregiver age and education; and measures of household consumption and food insecurity measured at baseline of the G2R trial.

Primary outcomes

Primary outcomes are domain-specific child development scores measured using the Bayley Scales for Infant and Toddler Development version III (BSID-III). The BSID-III assesses five domains of skill development: cognitive, language, motor, social-emotional, and adaptive behavior. Each domain will be examined as a separate primary outcome. Domains include a set of age-appropriate tasks that the child is asked to complete. The BSID-III will be adapted to the local context and a team of assessors will undergo three weeks of training prior to the start of assessments. For each domain, raw data will be converted to norm-referenced z-scores using the Bayley-III Scoring Assistant software.

Secondary outcome

Secondary outcomes are domain-specific child development scores measured using the Caregiver Reported Early Development Instruments (CREDI). Like the BSID-III, the CREDI assesses cognitive, language, motor, and social-emotional skills. While the BSID-III relies on direct assessments of children, the CREDI is based on caregiver reporting on child skills. Raw item data will be converted to norm-referenced z-scores for each domain using the CREDI scoring procedure [4].

References

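### Does planning effect estimates within the refugee and host strata, with no treatment-by-stratum contrast, leave the plan without a valid basis for comparing the two communities?

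*SAP*

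**What the plan says.** The Empirical strategy section sets out two analyses beyond the main intention-to-treat effect. The first concerns exposure before birth: "The investigators will also examine heterogeneity in treatment effects by the duration of program exposure" in utero. The second concerns the two communities: "The investigators will also estimate impacts within refugee and host (i.e., non-refugee) strata". The reason given for the second is "as the population of the G2R trial was drawn from these two communities".

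The Analysis section gives the model: "The investigators will fit a set of unadjusted and adjusted linear regression models to estimate average treatment effects". It adds that "All models will include variables used for stratification in the original randomization procedure". The treatment contrast is the pooled one ("The investigators will combine T1 and T2 groups into a single intervention group for the analysis"), compared with controls in the same villages. Under Primary outcomes there are five BSID-III domains, and "Each domain will be examined as a separate primary outcome".

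The SAP does not mention a product of treatment and community, a difference between the two stratum effects, or a test or interval for such a difference. It also does not say whether the stratum effects come from one model or two. It gives no alpha, power, sample size or stratum split for any analysis.

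**The concern.** Readers who see an effect for refugee children beside an effect for host children will compare them. Putting the stratification variables in the model adjusts for community but does not let the treatment effect vary by community, so that sentence does not supply the comparison. With no contrast fixed in advance, a reader may fall back on the common mistake of calling the effects different because one is significant and the other is not.

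The program could then be reported as helping children in one community but not the other when the true effects are the same. Five primary domains give several chances for this to happen. A pre-analysis plan is the natural place to rule it out, and one sentence would do so.

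**Working it through.** **No plan figure to reproduce.** The SAP states no number on this point. Everything below is illustration under assumptions: two-sided alpha 0.05, normal approximation, independent strata with sample shares f and 1−f, and the same true effect in both.

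**1. How often would a comparison by significance mislead?** Let d be the overall non-centrality, d = 1.960 + z(power). The stratum values are d√f and d√(1−f), with powers a and b. The chance that exactly one stratum is significant is a(1−b) + b(1−a).

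| Overall power | Split | d | a | b | Exactly one significant |
|---|---|---|---|---|---|
| no effect | any | 0 | 0.050 | 0.050 | 2 × 0.05 × 0.95 = 9.5% |
| 80% | 50:50 | 2.802 | 0.508 | 0.508 | 50.0% |
| 80% | 70:30 | 2.802 | 0.650 | 0.335 | 54.9% |
| 80% | 80:20 | 2.802 | 0.707 | 0.240 | 60.8% |
| 90% | 50:50 | 3.242 | 0.630 | 0.630 | 46.6% |
| 90% | 80:20 | 3.242 | 0.826 | 0.305 | 62.7% |
| 95% | 90:10 | 3.605 | 0.928 | 0.207 | 75.1% |
| 99.9% | 50:50 | 5.050 | 0.946 | 0.946 | 10.1% |
| 99.99% | 50:50 | 5.679 | 0.980 | 0.980 | 3.9% |

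An interaction test gives 5% in every row. The misleading rate is therefore large over ordinary power values. It has no firm range for this trial, though, because it moves from 3.9% to 75.1% with inputs the SAP does not state.

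**2. Does the plan lead to that comparison?** The two additional analyses are worded differently. Heterogeneity is the stated aim for exposure before birth. For the communities the aim is an impact in each, and the reason offered is where the sample came from. No hypothesis of a difference is stated, and no p-value rule appears anywhere in the document. The misreading in step 1 has to be supplied from outside the plan.

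**3. Are the planned outputs enough to make a valid comparison?** Two independent stratum estimates with their standard errors give the difference as estimate 1 minus estimate 2, with variance SE₁² + SE₂². Its confidence interval follows at once. The difference from a pooled model with an interaction term may vary slightly from this, because the pooled model shares covariate slopes across communities unless those are interacted as well. Both are valid contrasts.

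**4. What would naming the contrast gain?** Relative to the overall effect, the variance of the difference is 1/[f(1−f)], which is 4.0 at 50:50 and 6.25 at 80:20. For a difference as large as the overall effect, at 80% overall power:

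- 50:50: non-centrality 2.802 × √0.25 = 1.401, power 29%.
- 80:20: non-centrality 2.802 × √0.16 = 1.121, power 20%.

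The difference detectable with 80% power is 2.802/1.401 = 2.0 times the overall effect at 50:50, and 2.802/1.121 = 2.5 times at 80:20. Five independent null tests at 0.05 would give at least one false positive with probability 1 − 0.95⁵ = 22.6%. The contrast would have to be labelled exploratory and would usually be inconclusive.

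**The case for a change.** The strongest case for a change is that this document is the pre-analysis plan, so the model behind an announced stratum analysis belongs in it. Two effects per outcome will be reported, readers will compare them, and the usual shortcut misleads about half the time at conventional power. That a contrast can be computed afterwards is weak comfort, since choosing it after seeing the two results is what pre-specification is meant to prevent. The remedy costs a sentence and needs no new data.

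Much of this stands. The SAP names no contrast, the stratification covariates do not provide one, and a sentence would make the plan tidier. But the argument needs the plan to invite or permit a wrong conclusion if followed as written, and it does not. It yields a valid estimate in each community and makes no claim about their difference. With two strata and one treatment contrast, the choice of comparison is also narrow: it is the difference between two effects. Little room is left for choosing after the fact, beyond whether covariate slopes are shared.

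**Conclusion.** No change to the plan is needed. The omission is real, but it concerns a comparison the SAP never undertakes to make, in an analysis additional to the main one. The within-stratum estimates are valid. If the strata are independent, a valid difference and interval can be taken straight from them, so the plan does not lack a valid basis for comparison.

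The chance of discordant significance (about 50% at 80% overall power with equal strata, 3.9% to 75.1% across the cases shown) is a general property of subgroup p-values. It rests on an assumed alpha, power and split, and on a reader who compares by significance. A named contrast would have about 20-29% power, under the same assumptions and 80% overall power, for a difference as large as the overall effect. Competent analysts would either treat the two estimates as descriptive or report their difference with an interval, and the plan as written allows both.

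### Does group coaching in T2 make the pooled child-level regressions unsound because the plan names no standard-error method?

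*SAP*

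**What the plan says.** Under Randomization, the unit of assignment is the household: "Within treatment villages, participants were randomly assigned at the household-level to one of three intervention conditions or a control condition". T1 is described as "T1, “Individual, asset”: consumption support, cash asset transfer, coaching in individual household visits", and T2 as having "coaching in group setting and all other aspects of program". For the new study, "investigators will revisit T1, T2, and C1 households within treatment villages".

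Under Empirical strategy, "The investigators will combine T1 and T2 groups into a single intervention group for the analysis", on the ground that household economic impacts were alike in the two arms.

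Under Analysis, "The investigators will fit a set of unadjusted and adjusted linear regression models to estimate average treatment effects". The only design terms are those in "All models will include variables used for stratification in the original randomization procedure", and these variables are not listed. Child age and gender are covariates in the adjusted models, so each row is a child. The Background says the study will "assess children born during the intervention period", with no limit of one child per household. Nothing in the plan states that errors are independent, robust or clustered, and there is no random effect.

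**The concern.** Households coached together share a coach and one another's company. If coaching groups differ in how well they work, the scores of T2 children in the same group are correlated. That correlation arises after randomisation and in T2 only, so stratification terms, even village effects, do not remove it. Nor does clustering by household, the usual default when households are assigned. That T1 and T2 had similar average impacts says nothing about independence within a group. Siblings, if more than one per household is assessed, add a second and smaller source, in all arms.

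At stake would be standard errors that are too small, and intervals that are too narrow, for the five BSID-III domains and the CREDI scores.

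**Working it through.** The plan states no sample size, group size, correlation, number of villages or error rate, so there is no figure to reproduce. Every input below is an assumption.

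**Coaching groups, with no village variance left in the residual.** Take T1, T2 and C1 with *n* children each, unit variance, *m* assessed children per T2 coaching group and within-group correlation *r*.

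- Variance of the T2 mean: [1 + (m−1)r]/n. Variance of the T1 and C1 means: 1/n each.
- Variance of the pooled T1+T2 mean: [2 + (m−1)r]/(4n).
- True variance of pooled minus C1: [6 + (m−1)r]/(4n). Ordinary regression assumes 1.5/n = 6/(4n).
- Ratio of true to assumed variance: R = 1 + (m−1)r/6.
- Actual two-sided error at a nominal 5%: 2[1 − Φ(1.96/√R)]. Standard-error shortfall: 1 − 1/√R.

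| m | r | R | SE too small by | actual error |
|---|---|---|---|---|
| 3 | 0.01 | 1.003 | 0.2% | 5.04% |
| 3 | 0.05 | 1.017 | 0.8% | 5.2% |
| 5 | 0.01 | 1.007 | 0.3% | 5.1% |
| 5 | 0.05 | 1.033 | 1.6% | 5.4% |
| 10 | 0.01 | 1.015 | 0.7% | 5.2% |
| 10 | 0.05 | 1.075 | 3.6% | 5.9% |
| 20 | 0.01 | 1.032 | 1.5% | 5.4% |
| 20 | 0.05 | 1.158 | 7.1% | 6.9% |

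**Siblings.** If a share *s* of households has two assessed children with correlation *h*, R rises by 2sh/(1+s).

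- s = 0.03, h = 0.3: 0.018/1.03 = 0.017, error 5.2% on its own.
- s = 0.05, h = 0.5: 0.05/1.05 = 0.048, error 5.6% on its own.
- Both sources together, across the rows with m = 5 to 20: R from 1.024 to 1.206, error 5.3% to 7.4%.

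**If village is not in the model.** Assignment was within villages, so a village's common level largely cancels from the contrast, while an ordinary standard error still counts it. Let *v* be the between-village share of variance. With arms balanced in every village, R = 1 − v + (m−1)r/6. At v = 0.10:

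- m = 5, r = 0.01: R = 0.907, error 4.0%.
- m = 10, r = 0.05: R = 0.975, error 4.7%.
- m = 20, r = 0.05: R = 1.058, error 5.7%.

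The two effects offset exactly when (m−1)r = 6v = 0.6.

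**Simulation** (assumed 60 villages, one T2 group per village, v = 0.10, a random half of households with an eligible child, one child per household).

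- Village effects in the model, m = 5 to 20: ordinary errors 5.2–7.0%, household-clustered 5.2–6.9%, village-clustered 4.8–5.2%.
- No village effects, ordinary errors: from about 4.5% to around 5% for m = 5 and 10 (Monte Carlo error about 0.3 points), and 5.9–6.9% at m = 20 with r = 0.05.
- No group effect and no siblings, village effects in the model: 5.1% under all three.

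**Price of village clustering.** Degrees of freedom come from the number of villages: t(59)/1.96 = 1.021 and t(29)/1.96 = 1.043. Intervals are about 2% wider with 60 villages and 4% wider with 30.

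**The case for a change.** The best case for a change is that a standard-error method belongs in an analysis plan, that it determines every interval and p-value, and that naming it costs a sentence and closes a choice otherwise open after the data are seen. With village effects in the model, neither ordinary nor household-clustered errors cover the coaching groups, while village clustering stays near 5%. Wider assumptions also give larger errors: m = 25 with r = 0.10 gives R = 1.40 and 9.8%. Adding 30% two-child households with correlation 0.6 gives R = 1.677 and 13.0%.

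The omission stands, and so does the mechanism. Three things weaken the call for a change.

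- **Direction.** The shortfall is assured only if the models absorb village. The stratification variables are not listed, and without village among them ordinary errors can be right or conservative.
- **Extreme inputs.** Only children born in the intervention period count towards *m*. If half of households have such a child, m = 20 means coaching groups of 40 households and, with 60 villages, 60 × 3 × 20 = 3,600 assessed children. The 9.8% and 13.0% figures go further still.
- **Target of inference.** The figures treat coaching groups as a sample whose effects vary around an average. If the programme affects no child, there are no differing programme effects and the coaching part of the error vanishes. Whether intervals should extend to new groups or describe the programme as delivered is a choice.

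**Conclusion.** No change to the plan follows. This is a gap that analysts can fill sensibly, not a wrong rule: the Analysis section names a mean model and prescribes no faulty standard error, and the ordinary and household-clustered estimators tested above are suppositions.

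With equal arms, up to 10 assessed children per coaching group, correlation up to 0.05 and village in the models, the error rate is 5.1–5.9% instead of 5%, and standard errors are 0.3–3.6% too small. Without village in the models there is little or no excess. Only m = 20 with r = 0.05 departs clearly from nominal. Siblings are possible but not stated, and at 3–5% two-child households they alone give 5.2–5.6%.

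Nor is there one agreed remedy. Household assignment within villages does not itself require village clustering. Clusters by coaching group in T2 and by household elsewhere are an equally defensible choice. Village clustering widens intervals by 2–4%, about as much as the shortfall it repairs at 5 to 10 children per group, and it covers the coaching groups only if they were formed within villages, which the plan does not say. The choice can be settled once group sizes and the stratification variables are in hand.

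### Does the plan need to say whether the strata-only or the covariate-adjusted model is the primary one?

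*SAP*

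**What the plan says.** Under Analysis, the SAP states: "The investigators will fit a set of unadjusted and adjusted linear regression models". The unadjusted model is not bare, since "All models will include variables used for stratification in the original randomization procedure". The adjusted model adds child age and gender, caregiver age and education, and baseline household consumption and food insecurity. The reason given is: "Adjusted models will include the following additional covariates to improve precision".

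Under Primary outcomes there are five BSID-III domains, and "Each domain will be examined as a separate primary outcome". With two models each, that makes 5 × 2 = 10 candidate primary estimates.

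The Empirical strategy section speaks of a main analysis but settles other matters. It fixes an intention-to-treat comparison for all outcomes and says that "The investigators will combine T1 and T2 groups into a single intervention group for the analysis". It does not say which regression supplies the main result.

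**The concern.** A pre-analysis plan exists largely to fix the deciding analysis before the data are seen. This one lists two models for each primary outcome and gives no rule for a disagreement. If one p-value falls below the threshold and the other above it, the authors could put the claim on whichever is favourable. The error rate for that domain would then exceed the nominal one, and the headline estimate and interval would also have been chosen after the fact. The same choice recurs in all five domains.

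**Working it through.** The SAP states no significance level, power, sample size or effect size, so it has no figure of its own to reproduce. The check rests on assumptions.

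**Assumptions.** Two-sided alpha is 0.05 (critical value 1.96). R² is the share of outcome variance, beyond the strata, that the added covariates explain. It is varied from 0.02 to 0.30, and the SAP favours no part of that range. Covariates are taken as unaffected by assignment.

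**Formula.** In large samples the strata-only and adjusted test statistics are bivariate normal with correlation √(1 − R²). If the adjusted statistic has mean m, the strata-only statistic has mean m√(1 − R²). Under no effect, the chance that at least one model is significant is 1 − P(|Z₁| ≤ 1.96 and |Z₂| ≤ 1.96). For 80% power of the adjusted model, m = 1.96 + 0.84 = 2.80.

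| R² | Correlation | No effect: either significant | 80% power: adjusted alone | 80% power: strata-only alone |
|---|---|---|---|---|
| 0.02 | 0.990 | 5.7% | 2.0% | 1.2% |
| 0.05 | 0.975 | 6.0% | 3.7% | 1.7% |
| 0.10 | 0.949 | 6.5% | 6.3% | 2.0% |
| 0.20 | 0.894 | 7.1% | 11.5% | 2.3% |
| 0.30 | 0.837 | 7.6% | 17.4% | 2.3% |

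The excess over 5% under no effect is therefore 0.7 to 2.6 percentage points per domain.

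**Which disagreements matter.** If the adjusted model were named primary, every trial in the adjusted-alone column would keep its claim. Only the last column would change.

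**Finite samples.** The formula ignores the cost of fitting the covariates, which shows most at low R². A least-squares simulation (assumed n = 600, 2:1 allocation, six covariates, 20,000 trials) gives about 1.7% for strata-only alone at R² = 0.02 and 2.0% at R² = 0.05, against 1.2% and 1.7% in the table. At n = 300 both are about 2.5%; at n = 2,000 they are 1.4% and 1.6%. The table entries are thus large-sample values and not strict bounds, and about 2% is a fair summary at 80% power. At 50% power (m = 1.96) the large-sample range is 1.9% to 4.2%.

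**Would naming a model fix one result?** The adjusted model is described by kinds of variable. The SAP does not say which consumption and food-insecurity measures enter, or whether child age and caregiver education are linear or categorical. The strata-only model has fewer open choices. A sentence naming the adjusted model as primary would still leave several versions of it.

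**The case for a change.** The strongest case for a change is that choosing the deciding model is ordinary SAP content and not something left to a protocol. It would cost two sentences, and the choice arises five times. With independent domains, the chance of at least one false positive is 1 − 0.95⁵ = 0.226 with one model per domain. If either model may count, it becomes 1 − (1 − 0.0604)⁵ = 0.268 at R² = 0.05 and 0.325 at R² = 0.30. With a between-domain correlation of 0.5, simulation gives 0.182 rising to 0.215 and 0.263.

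The arithmetic stands, and so does the observation that no model is labelled primary. Three things limit its force. First, most of those totals comes from testing five domains without a multiplicity rule, which is a separate matter that naming a model leaves untouched. Second, the increment is what would arise if the favourable result were taken in every disagreement, in every domain, although the plan commits the authors to fitting both models and their purpose is stated. When both are reported, a reader sees any disagreement. Third, the proposed sentence alone would not settle the result, for the reason given in the check.

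**Conclusion.** No change follows. The plan leaves out a label, and analysts who follow it as written still obtain sound estimates: two pre-announced regressions, both conditioned on the strata, both aimed at the same intention-to-treat contrast, with precision given as the reason for the fuller one. A sensible analyst would lead with the adjusted result and show the strata-only result beside it.

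The most that selective emphasis could add is about 0.7 to 2.6 points per domain to a 5% false-positive rate. At 80% power, naming the adjusted model would alter a claim in about 2% of trials. These sizes rest on an assumed two-sided 0.05, an assumed R² of 0.02 to 0.30, covariates unaffected by assignment, and, for the simulation, assumed sample sizes and allocation. Choosing the label, the household measures and the codings before the outcome data are analysed by arm would be good practice, but the validity of the planned analysis does not depend on writing it into this document.

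### The adjusted models, built for precision, leave out assessor although a team of assessors scores the five primary BSID-III domains; adding it is a cheap, modest gain

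*SAP*

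**What the plan says.** Under Primary outcomes, the SAP takes each of five BSID-III domains as a separate primary outcome. More than one person scores them: "a team of assessors will undergo three weeks of training prior to the start of assessments". The Secondary outcome section contrasts the two instruments: "While the BSID-III relies on direct assessments of children, the CREDI is based on caregiver reporting on child skills". For scaling, "raw data will be converted to norm-referenced z-scores using the Bayley-III Scoring Assistant software".

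Under Analysis, "The investigators will fit a set of unadjusted and adjusted linear regression models to estimate average treatment effects". Two sets of terms are named:

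- In every model: "All models will include variables used for stratification in the original randomization procedure". These variables are not listed.
- In the adjusted models only: "Adjusted models will include the following additional covariates to improve precision: child age in months and gender; caregiver age and education", together with "measures of household consumption and food insecurity measured at baseline of the G2R trial".

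Assessor is in neither set by name. The stratification variables were fixed for the earlier trial, before any child was assessed for this study, so they cannot include assessor itself. Under Randomization, "Within treatment villages, participants were randomly assigned at the household-level to one of three intervention conditions or a control condition". Intervention and C1 households therefore sit in the same villages.

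**The concern.** When several people administer and score a directly observed test, some of the score variance reflects who did the scoring. Training reduces that part, but the SAP does not show that it removes it. Conversion to norm-referenced scores does not remove it either, because external norms treat all assessors alike.

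The adjusted models exist to gain precision, and assessor is a source of outcome variance known from the design. What is at stake is interval width on all five primary domains. There is also a reason to settle it in advance: adding assessor after the data are seen would be a post hoc modelling choice repeated over five primary outcomes.

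**Working it through.** The SAP states no sample size, power, standard deviation or assessor variance, so there is no figure of its own to reproduce. Everything below rests on assumed values, shown as a range.

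**Inputs.** From the SAP: more than one assessor, linear regression, no assessor term, household-level allocation within villages. Assumed: the share ρ of residual variance due to assessor (2%, 5%, 10%); K = 10 assessors; n = 900 or 300 children.

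**Step 1, gross effect.** With assessor crossed with arm, the standard error (SE) without assessor divided by the SE with assessor is 1/√(1 − ρ):

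- ρ = 2%: 1/√0.98 = 1.010
- ρ = 5%: 1/√0.95 = 1.026
- ρ = 10%: 1/√0.90 = 1.054

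The reciprocals, 0.990, 0.975 and 0.949, are the factors by which indicators would shrink the SE if they cost nothing. As an illustration of the gross effect, take a design with 80% power with assessor in the model (assumed effect 0.2 SD, two-sided alpha 0.05, 2:1 allocation). Without the term its power is 79.3%, 78.0% and 75.8%.

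**Step 2, cost of the indicators.** If assessors do not differ and are spread at random over children, the K − 1 = 9 indicators inflate the SE by about √((n − 1)/(n − K)):

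- n = 900: √(899/890) = 1.005, a cost of 0.5%
- n = 300: √(299/290) = 1.015, a cost of 1.5%

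**Step 3, net effect.** Step 1 divided by step 2 gives the SE without assessor relative to the SE with it:

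| ρ (assumed) | n = 900 | n = 300 |
|---|---|---|
| 2% | 1.010/1.005 = 1.005 | 1.010/1.015 = 0.995 |
| 5% | 1.026/1.005 = 1.021 | 1.026/1.015 = 1.010 |
| 10% | 1.054/1.005 = 1.049 | 1.054/1.015 = 1.038 |

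The break-even share is ρ = (K − 1)/(n − 1): 9/899 = 1.0% at 900 children and 9/299 = 3.0% at 300.

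**Step 4, simulation check.** The setting was 900 children, 10 assessors, 45 villages and 400 runs, with assessors spread at random over children. The reported SE without assessor was 1.8% larger at ρ = 5% and 4.2% larger at ρ = 10%. At ρ = 0 the indicators cost about 0.5%, as in step 2. The simulated gains are a little below the table, as expected when only 10 assessors are drawn.

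**Step 5, assessors working by village.** In the same simulation with assessors allocated by village, the reported SE without assessor was 2.4% larger at ρ = 5% and 4.7% larger at ρ = 10%. Village fixed effects removed the whole excess. The actual spread of the estimates was the same with and without assessor (0.0642 both ways at ρ = 10%), because each village had the same split between arms. In that setting omission makes the interval too wide but does not move the estimate.

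**The case against.** The strongest reply is that nothing is stated wrongly. The listed covariates are sensible, leaving one out does not invalidate the estimate, and the SAP already names three weeks of training as a safeguard. That stands, and it is why this is a suggestion and not an error. It does not remove the point, because the covariate list is fixed in this document and its declared purpose is precision.

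The second reply is that the gain is assumed and small. This also stands. The gross figures charge nothing for the indicators, and at a 2% share the net effect changes sign between 900 and 300 children.

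Four stronger readings are tempting, and the SAP does not support them:

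- *Nothing in the planned model deals with assessor differences.* The stratification variables are not listed. If they include village or area and assessors work by area, they would absorb some or all of the assessor variance (step 5). The SAP states neither condition, so this can be neither credited nor excluded.
- *Chance imbalance of assessors across arms biases the treatment effect.* Chance imbalance is sampling variability that the SE already reflects. Only assignment that depends on arm would bias the contrast, and the SAP does not suggest it.
- *Silence on how assessors are assigned is a defect.* Fieldwork allocation is commonly left to the protocol, which is not at hand. It enters here only as a condition: assessor is determined after randomisation, so adjusting for it is safe only if assignment does not depend on arm.
- *CREDI has the same problem.* The SAP says that CREDI is caregiver-reported, but not who administers it or whether several interviewers do.

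**Conclusion.** The point holds as a modest matter of precision. A team scores the primary outcomes, the covariate list meant to improve precision omits assessor, and any assessor variance left over after the stratification terms widens the intervals.

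Under assumed shares of 5% to 10%, and at an assumed 900 children and 10 assessors, the net gain in SE is about 2% to 4%. At a 2% share it is about nil, and it shrinks further as the number of children per assessor falls. It also shrinks, possibly to nothing, if the stratification variables already stand in for the areas that assessors cover. None of these quantities can be read from the SAP. The omission does not bias the planned estimate so long as assessors are not assigned according to arm. Priority is low.

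**What to change.** - Add assessor indicators to the adjusted models for all five BSID-III domains, named in the SAP before the data are analysed.
- Record the assessor ID with each assessment.
- State that assessors are assigned independently of arm and that each sees both intervention and C1 children. Allocation by household within villages makes this feasible.
- Apply the same to CREDI, with interviewer indicators, only if several interviewers administer it.

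The cost is one model term and one recorded field, with no extra staff or visits. The statistical downside is a few degrees of freedom: about 0.5% (900 children) to 1.5% (300 children) of the SE with 10 assessors who do not differ. If the number of children per assessor turns out to be small, the break-even share in the working shows whether the term is worth including. That decision should be made from the counts alone, before outcomes are seen.
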